#### 5.4.2 Axitinib dose modification

If a patient experiences a CTCAE grade 3 or higher and/or unacceptable toxicity (any grade), where the clinician considers the event of concern to be specifically associated with axitinib (and not attributable to the disease, disease-related processes for which patient is being treated, or to avelumab), dosing will be interrupted and supportive therapy administered as required in accordance with local practice/guidelines. If the toxicity resolves or reverts to  $\leq$ CTCAE grade 2 within 3 weeks of onset, treatment with axitinib may be restarted at the same dose or a lower dose using the rules below for dose modifications. There will be no individual modifications to dosing schedule in response to toxicity, only potential dose reduction or dose interruption. If the toxicity does not resolve to  $\leq$ CTCAE grade 2 after 3 weeks, then the patient should be withdrawn from the study and observed until resolution of the toxicity.

**Table 5.** Axitinib Dose interventions

Intervention	Axitinib dose
Starting dose	5 mg orally BID
Level -1	3 mg orally BID
Level -2	2 mg orally BID

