
(n=2 related to avelumab), and presyncope, spinal cord compression, and hypoxia (all n=2, not related to study treatment). Ten (18%) of 55 patients discontinued one or both study drugs due to adverse events. Seven (13%) of 55 discontinued avelumab, with increased alanine aminotransferase concentration being the only adverse event leading to discontinuation in more than one patient (n=3 [6%]). Four (7%) of 55 patients discontinued axitinib (no events occurred in more than one patient). Six (11%) of 55 patients died before data cutoff: five (9%) due to disease progression (four after the end of treatment) and one (2%) due to treatment-related autoimmune myocarditis. 32 (58%) of 55 patients had avelumab dose delays, with duration of 7 days or longer in 25 (46%) of 55 patients. Four (7%) of 55 patients received less than 90% of the planned avelumab dose in one infusion because of adverse events: three due to infusion-related reactions (one of whom discontinued treatment) and one due to an electrocardiogram abnormality unrelated to study treatment. Axitinib was decreased at least once in 31 (56%) of 55 patients and increased at least once in ten (18%) of 55 patients. Axitinib dose reductions were due to adverse events in 28 (51%) of 55 patients, among whom the most common (in >5% of patients) were palmar-plantar erythrodysaesthesia syndrome (n=6), fatigue (n=5), hypertension (n=4), and proteinuria (n=3).

Table. Treatment-related adverse events occurring in  $\geq 10\%$  of patients

Table 2

	All grades	Grade 3	Grade 4	Grade 5
All events	53 (96%)	26 (47%)	5 (9%)	1 (2%)
Diarrhoea	32 (58%)	2 (4%)	0	0
Dysphonia	26 (47%)	0	0	0
Hypertension	26 (47%)	16 (29%)	0	0
Fatigue	25 (46%)	2 (4%)	0	0
PPE syndrome	17 (31%)	4 (7%)	0	0
ALT increased	16 (29%)	4 (7%)	0	0
Rash	16 (29%)	1 (2%)	0	0
AST increased	14 (26%)	1 (2%)	0	0
Hypothyroidism	14 (26%)	0	0	0
Amylase increased	13 (24%)	3 (6%)	1 (2%)	0
Decreased appetite	13 (24%)	1 (2%)	0	0
Mucosal inflammation	13 (24%)	1 (2%)	0	0
Infusion-related reaction*	11 (20%)	1 (2%)	0	0
Lipase increased	11 (20%)	1 (2%)	3 (6%)	0
Nausea	11 (20%)	1 (2%)	0	0
Arthralgia	9 (16%)	1 (2%)	0	0
Weight decreased	9 (16%)	1 (2%)	0	0
Pruritus	8 (15%)	0	0	0
Dysgeusia	7 (13%)	0	0	0
Stomatitis	7 (13%)	0	0	0
Dyspnoea	6 (11%)	0	0	0
Myalgia	6 (11%)	0	0	0
Proteinuria	6 (11%)	2 (4%)	0	0
Vomiting	6 (11%)	0	0	0
Hypophosphataemia	5 (9%)	2 (4%)	0	0
Blood triglycerides increased	4 (7%)	1 (2%)	0	0
Dehydration	3 (6%)	1 (2%)	0	0
Pain in extremity	3 (6%)	1 (2%)	0	0

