## Proprietary of MD Anderson Cancer Center

axitinib since single agent activity has been reported with this agent in ACC. Guidance for management of the most common overlapping adverse events are outlined below:

- Diarrhea:

Grade 1-2: manage with anti-diarrheal agents (E.g., loperamide). If no improvement dose-reduce/hold axitinib first, if no improvement hold avelumab (management as per Table 4), if improvement, axitinib can be re-started.

Grade  $\geq 3$ : hold both drugs, discard an infectious agent, and treat with anti-diarrheal agents and steroids as per Table 4. Re-start with single agent axitinib.

- Fatigue:

Grade  $\geq 2$ : Hold avelumab first, if no improvement dose-reduce axitinib, if improvement avelumab can be re-started. If only single agent can be tolerated, prioritize axitinib.

- Hypertension

- Hold Axitinib when unable to control blood pressure to  $<140/90$  on greater than 4 Blood pressure medications from multiple classes on maximally tolerated doses.
- Qtc-Hold for  $Qtc > 500$ msec, for  $Qtc$  from 470-499msec, Cardiology collaborator will evaluate and review for drug interactions and presence of underlying structural heart disease, and resume when  $Qtc$  by EKG interpretation shows normal  $Qtc$

- Transaminitis (increase in ALT and/or AST):

Grade 1-2: Hold avelumab first, if no improvement, dose-reduce/discontinue axitinib, if improvement avelumab can be re-started

Grade  $\geq 3$ : hold both drugs, discard an infectious agent, and treat with steroids as per Table 4. Re-start with single agent axitinib.

Other overlapping AEs:

- Decreased appetite, nausea, weight loss, vomiting, dyspnea, arthralgia, stomatitis are more common with axitinib, therefore, dose reductions of these agent should precede avelumab hold.
- Rash, hypothyroidism, asthenia and hematologic toxicities should be initially attributed to avelumab and managed accordingly (Tables 3 and 4), if no improvement by avelumab hold, axitinib dose-reduction/discontinuation should follow.

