#### 5.4.1 Avelumab

Every effort should be made to administer each of the investigational products at the planned dose and schedule. No avelumab dose modifications are permitted in this study, but the next administration of investigational product may be omitted based on persisting toxicity, as outlined in the next tables.

**Table 3.** Treatment Modification for Symptoms of Infusion-Related Reactions

NCI-CTCAE Grade	Treatment Modification for Avelumab
Grade 1 – mild Mild transient reaction; infusion interruption not indicated; intervention not indicated.	Decrease avelumab infusion rate by 50% and monitor closely for any worsening.
Grade 2 – moderate Therapy or infusion interruption indicated but responds promptly to symptomatic treatment (for example, antihistamines, NSAIDs, narcotics, IV fluids); prophylactic medications indicated for $\leq 24$ h.	Temporarily discontinue avelumab infusion. Resume infusion at 50% of previous rate once infusion-related reaction has resolved or decreased to at least Grade 1 in severity, and monitor closely for any worsening.
Grade 3 or Grade 4 – severe or life-threatening Grade 3: Prolonged (for example, not rapidly responsive to symptomatic medication and/or brief interruption of infusion); recurrence of symptoms following initial improvement; hospitalization indicated for clinical sequelae. Grade 4: Life-threatening consequences; urgent intervention indicated.	Stop avelumab infusion immediately and disconnect infusion tubing from the subject. Subjects have to be withdrawn immediately from study drug treatment and must not receive any further study drug treatment.

 
-If avelumab infusion rate has been decreased by 50% or interrupted due to an infusion reaction, it must remain decreased for the next scheduled infusion. If no infusion reaction is observed in the next scheduled infusion, the infusion rate may be returned to baseline at the subsequent infusions based on investigator's medical judgment.
 
- If hypersensitivity reaction occurs, the subject must be treated according to the best available medical practice.
 
	

IV = intravenous; NCI-CTCAE = National Cancer Institute-Common Terminology Criteria for Adverse Event; NSAIDs = nonsteroidal anti-inflammatory drugs.

Table 4. Management of Immune-mediated Adverse Reactions

Gastrointestinal irAEs		
Severity of Diarrhea/Colitis (NCI-CTCAE v4.03)	Initial Management	Follow-up Management

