## 5.9 Treatment duration

Subjects will continue treatment until confirmed disease progression, unacceptable toxicity, refusal to participate further, or loss to follow-up. Patients with evidence of disease progression per RECIST 1.1 (see appendix 1), who were still experiencing clinical benefit could be considered for continuation of treatment as per the investigator's clinical judgment and after discussion between the investigator and study Supporter.

If patients develop unacceptable toxicity attributed to one of the study treatments leading to discontinuation, they could continue receiving the other study treatment.

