# Proprietary of MD Anderson Cancer Center

EKG	X			
Echocardiogram	X	X 		
Urine analysis for proteinuria	X	X 		
Pregnancy Test (serum or urine) for all women of child bearing potential 	X	X 		
Radiology & Tumor Measurements 	X	X Every 8 weeks, ± 7 days		X
Biopsy	X If archived tissue not available			
Blood-based biomarkers	X 	X 		
Study Drug Compliance		X At each clinic visit		
Subsequent Anticancer Therapy				X
Survival Status				X

1 Written informed consent will be given by each patient prior to undergoing protocol specific evaluation and prior to receiving treatment

2 Chemistry profile includes: BUN, creatinine, sodium, potassium, carbon dioxide, magnesium, total bilirubin, alkaline phosphatase, aspartate aminotransferase, alanine aminotransferase, total protein, and serum phosphorus

3 Serum or urine pregnancy test will be obtained at baseline within 7 days prior to treatment and monthly during treatment in all women of child bearing age and again if clinically indicated

4 CT scan, PET CT scan of the chest/abdomen/pelvis and/or MRI of base of skull/orbit/face as clinically indicated. CT scan or MRI of the brain if clinically indicated

5 Long term follow-up will occur every 6 months by medical/clinical data review or phone contact

6 For patients who discontinue treatment due to reasons other than disease progression, tumor assessment will continue as per during the treatment schedule (i.e. radiology & tumor measurements every 8 weeks +/- 7 days).

7 Extended safety follow up: given the potential risk of immune-related toxicity, safety follow up will be performed up to 90 days after the last dose of avelumab administration. The extended follow up beyond 30 days after last avelumab administration may be performed either via a site visit or via a telephone call with subsequent site visit requested in case any concerns noted during the telephone call

8 Blood will be collected on at baseline (pre-treatment), day 7 (optional), day 15, prior to C3D1, and at progression (optional). Three categories of specimen will be collected: EDTA Vacutainer (checkpoint markers/CAFs): 10 mL = 1 x 10 mL; Streck CF-DNA BCT (ctDNA): 10 mL = 1 x 10 mL; and Sodium Heparin (immunoprofiling): 60 mL = 6 x 10 mL. All blood will be collected and processed by the Thoracic Research Team ([name] laboratory) according the institutional and laboratory standard operating procedures (SOPs).

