#### Subjective Progression

Patients requiring discontinuation of treatment without objective evidence of disease progression should not be reported as PD on tumor assessment CRFs. This should be indicated on the end of treatment CRF as off treatment due to Global Deterioration of Health Status. Every effort should be made to document PD even after discontinuation of study treatment.

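### Section 5.4.2 takes a patient with unresolved axitinib toxicity off the study; read literally, this conflicts with the rules that keep tumor assessment going after treatment stops

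*Combined protocol and SAP*

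**What the plan says.** Section 5.4.2 applies to toxicity of grade 3 or higher, or unacceptable toxicity of any grade, that the clinician attributes specifically to axitinib and not to avelumab. Dosing is interrupted. If the event has not come down to grade 2 or lower after 3 weeks, "then the patient should be withdrawn from the study and observed until resolution of the toxicity".

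Other parts of the same document bear on that patient:

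- Section 6, Table 6, footnote 6: "For patients who discontinue treatment due to reasons other than disease progression, tumor assessment will continue" on the treatment schedule, every 8 weeks ± 7 days.
- Section 6, Table 6, footnote 5: "Long term follow-up will occur every 6 months by medical/clinical data review or phone contact". Footnote 7 extends safety follow-up to 90 days after the last avelumab dose.
- Appendix 1, Subjective Progression: "Every effort should be made to document PD even after discontinuation of study treatment".
- Section 5.9: patients who stop one drug for toxicity attributed to it may stay on treatment; "they could continue receiving the other study treatment".
- Section 5.4.3: uncontrolled grade 4 hypertension leads to stopping axitinib. Leaving the study is not mentioned.
- Section 5.4.1, Table 3 (grade 3 or 4 infusion reactions): "Subjects have to be withdrawn immediately from study drug treatment and must not receive any further study drug treatment".

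**The concern.** Stopping a drug and leaving a study are different events. Table 3 and Section 5.4.3 show that the protocol can name the narrower one. Section 5.4.2 names the wider one, and the only follow-up it mentions is of the toxicity. No text reconciles it with footnote 6 or Section 5.9.

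Three outputs are exposed if a site takes the sentence at its word:

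- **Response.** Appendix 1 requires CR and PR to be confirmed by two measurements at least 4 weeks apart, and scans are 8 weeks apart. A patient withdrawn after a first response and before the next scan has no confirmed response.
- **PFS and duration of response.** Section 9.2 estimates both by Kaplan-Meier. If assessment ends at withdrawal and the patient is censored there, censoring is triggered by a treatment-related event and may be informative.
- **Treatment.** The patient may lose access to avelumab that Section 5.9 would allow.

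Survival status is least exposed, because it comes from record review or a phone call.

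**Working it through.** **Step 1. Compare the rules for one patient** whose axitinib-attributed toxicity is still above grade 2 at 3 weeks, without progression.

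| Meaning given to the 5.4.2 wording | Footnote 6 and Appendix 1 (scans) | Section 5.9 (other drug) |
|---|---|---|
| Off the study | conflict | inconsistent |
| Off study treatment | no conflict | inconsistent unless a deliberate exception |
| Off axitinib only | no conflict | consistent |

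Only the last meaning fits everything, and the text does not state it. An example on the protocol's timing: toxicity starts in week 6, the week 8 scan shows a first PR, and the 3 weeks run out in week 9. The confirming scan is due in week 16. Under footnote 6 it is done; under a literal 5.4.2 it is not.

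**Step 2. Reproduce the design (Section 9.2).** Stop if 0/10 respond; reject if ≤3/29 respond.

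P(accept) = Σ over x = 1..10 of Bin(x; 10, p) × P(Bin(19, p) ≥ 4 − x).

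- p = 0.05: early stop 0.599, P(accept) 0.047, expected N 17.6.
- p = 0.20: early stop 0.107, power 0.801, expected N 27.0.

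These match the plan.

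**Step 3. How many patients.** Section 1.4 reports that 4 of 55 patients (7.3%) in the renal study of this combination stopped axitinib for adverse events. The exact 95% CI is 2.0% to 17.6%.

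- 30 × 4/55 = 2.2 patients (CI limits × 30: 0.6 to 5.3).
- That count has no 3-week or above-grade-2 filter. If half qualify (assumption), 30 × 2/55 = 1.1.

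**Step 4. Effect on power, affected patients counted as non-responders.** Let q be the share affected and f the share of their responses lost before confirmation (assumed, and independent of response). Counted response rate = 0.20 × (1 − q·f). Section 9.1 analyses all eligible enrolled patients, up to 30, while the 9.2 rule is written for 29, so both are shown. The cut-off of 3 for 30 patients is an assumption; the protocol gives none.

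| q | f | counted rate | power, n = 29 | power, n = 30, cut-off 3 |
|---|---|---|---|---|
| 0 | – | 0.2000 | 0.801 | 0.814 |
| 2/55 | 0.5 | 0.1964 | 0.789 | 0.803 |
| 2/55 | 1 | 0.1927 | 0.777 | 0.791 |
| 4/55 | 0.5 | 0.1927 | 0.777 | 0.791 |
| 4/55 | 1 | 0.1855 | 0.751 | 0.766 |

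At the upper confidence limit (q = 0.176) with n = 29, power is 0.739 for f = 0.5 and 0.664 for f = 1.

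**Step 5. Affected patients called non-evaluable instead.** With two such patients, both in stage 2, 30 − 2 = 28 remain. Replacing 19 by 18 in the formula and keeping the cut-off at 3 gives power 0.786.

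**The case against.** The best reply is that the document can be read as a whole. Section 5.4.2 is a dosing section, and footnote 6 is the specific rule on scans after treatment stops, so the specific rule should govern and the 5.4.2 wording should be taken as loose language for leaving treatment. On that reading the scan conflict disappears. This is a fair account of the likely intent, but it does not cure the instruction: a coordinator who works from 5.4.2 is told to take the patient off the study.

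Four stronger readings are tempting, and the documents do not support them.

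- *That 5.4.2 limits follow-up to the toxicity.* The sentence sets how long the toxicity is observed. It does not say that nothing else is followed; the loss of scans is inferred from the withdrawal wording.
- *That 5.4.2 removes the Section 5.9 option.* Section 5.9 still stands and is permissive, and 5.4.2 may be a deliberate limit on it. Section 5.4 asks for effort to continue "axitinib since single agent activity has been reported with this agent in ACC", and Section 1.1 reports no responses in ACC to single-agent pembrolizumab. Stopping both drugs is a plausible intention, but it is not written down.
- *That power is materially harmed.* The share affected and the share lost are guesses. The 4/55 figure is probably too high for this rule, because overlapping toxicities, QTc and hypertension have their own instructions in Sections 5.4 and 5.4.3.
- *That informative censoring is built into the plan.* Sections 9.1 and 9.2 give no censoring rule, so it is a possibility only.

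The undefined term evaluable in Section 9.2 is a separate matter. It comes in here only because it leaves open how such a patient would be counted.

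**Conclusion.** The wording is wrong as it stands. Read literally, Section 5.4.2 conflicts with footnote 6 and Appendix 1 and is inconsistent with Sections 5.9 and 5.4.3, and nothing resolves this. That conclusion rests on the text alone.

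The consequence is modest: perhaps 1 to 2 of 30 patients, assuming that the renal-study rate carries over and that between half and all of those events meet the 3-week rule. Power falls by roughly 1 to 5 percentage points on either denominator (0.801 to 0.751–0.789 on 29; 0.814 to 0.766–0.803 on 30), with a larger fall only at the upper confidence limit. Responses confirmed before withdrawal are untouched. The reason to act is that a treatment-related event could end outcome assessment, not that the design fails.

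**What to change.** In Section 5.4.2, replace withdrawal from the study with one of two wordings, according to what the sponsor intends:

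- **Both drugs stop:** *the patient should be withdrawn from study treatment*, with this exception also stated in Section 5.9.
- **Avelumab stays available:** *axitinib should be permanently discontinued; avelumab may continue as described in Section 5.9*.

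Under either, keep the observation of the toxicity and add: *Tumor assessments (footnote 6), long-term follow-up (footnote 5) and 90-day safety follow-up (footnote 7) continue.* The choice about avelumab is treatment policy and belongs to the sponsor; continued follow-up is the needed correction.

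The cost is a sentence or two in 5.4.2 and, under the first option, a short exception in 5.9. No visits or scans are added, because footnotes 5 to 7 already schedule them. The sample size and the decision rule do not change.

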therapy directly per protocol. Patients in the dose-finding cohort received a median of 32·5 avelumab infusions (IQR 31·0–37·0) during a median follow-up of 69·7 weeks (IQR 66·1–74·1). The median duration of treatment was 66·6 weeks (IQR 66·0–74·1) with axitinib and 66·0 weeks (IQR 65·6–74·0) with avelumab. Among the six patients in the dose-finding cohort, four (67%) had a grade 3 or 4 treatment-related adverse event (grade 3 hypertension, palmar-plantar erythrodysaesthesia, proteinuria, and mucosal inflammation and grade 4 increase in lipase concentration). One patient had a dose-limiting toxicity (grade 3 proteinuria) that led to axitinib dose reduction and resolved without sequelae; this patient continued treatment with avelumab at 10 mg/kg and 3 mg axitinib twice daily. One patient discontinued axitinib due to grade 3 palmar-plantar erythrodysaesthesia syndrome. This patient continued treatment with avelumab monotherapy until disease progression. At the end of the dose-finding phase, the maximum tolerated dose established for the combination was avelumab 10 mg/kg every 2 weeks and axitinib 5 mg twice daily. There was no differences in antitumor activity or safety between patients in either phase who received lead-in treatment with axitinib and those who did not. At the cutoff of April 13, 2017, the median follow-up for all 55 patients was 52·1 weeks (IQR 37·4–56·1). 54 (98%) patients received avelumab and axitinib, and one patient received only axitinib because of an adverse event (grade 3 increase in blood creatine phosphokinase concentration) that arose before avelumab was started. At the time of cutoff, combination treatment was ongoing in 29 (53%) of 55 patients, two (4%) were receiving treatment with axitinib alone, and one (2%) was receiving avelumab alone. Patients received avelumab for a median of 37·0 weeks (IQR 14·0–50·0) and axitinib for a median of 36·0 weeks (IQR 18·1–50·1). Reasons for treatment discontinuation were progressive disease (n=11 for avelumab and n=14 for axitinib), adverse events (n=7 for avelumab and n=4 for axitinib), withdrawal of consent (n=3 for both treatments), death (n=2 for both treatments), and physician's decision (n=1 for both treatments). All 55 patients experienced at least one adverse event during the trial, and 53 (96%) had one or more adverse events that were judged by the investigator to be related to avelumab or axitinib. The most frequent treatment-related adverse events (occurring in  $\geq 10\%$  of patients) included diarrhea, hypertension, dysphonia, fatigue, palmar-plantar erythrodysaesthesia syndrome, increased alanine aminotransferase concentration, rash, increased aspartate aminotransferase concentration, hypothyroidism, increased amylase concentration, decreased appetite, mucosal inflammation, infusion-related reactions, increased lipase concentration, and nausea. 32 (58%) of 55 patients had grade 3 or worse treatment-related adverse events and one died from treatment-related autoimmune myocarditis (confirmed by widespread myocarditis on post-mortem histopathology; viral cause was excluded). 16 (29%) of 55 patients reported infusion-related reactions, most of which were grade 1 or 2; one (2%) patient had a grade 3 infusion-related reaction and discontinued avelumab, and one (2%) additional patient had chills unrelated to treatment. 16 (29%) of 55 patients had infusion-related reactions with the first infusion, and one (2%) had three grade 2 infusion-related reactions at cycles eight, nine, and ten, but continued treatment beyond cycle ten until disease progression. 23 (42%) of 55 patients had immune-related adverse events; see appendix for adjudication criteria. The most frequent was hypothyroidism in 13 (24%) patients, and five (9%) had grade 3 or worse immune related events, which led to avelumab dose interruption in one patient (due to rash) and discontinuation of Avelumab in the other four patients. 20 (36%) of 55 patients had serious adverse events, which were judged to be treatment related in 12 (22%). Serious adverse events occurring in more than one patient were increased alanine aminotransferase concentration (n=2, deemed to be treatment related), infusion-related reactions

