### **9. Statistical Consideration**

#### 9.1 Definitions

All efficacy analyses will be performed in all eligible patients enrolled. Safety analyses will be performed on all patients who received any dose of any treatment.

1. Objective Response Rate (ORR) is the percent of patients whose best response is complete response or partial response as determined by RECIST 1.1 criteria.
2. irORR is the percent of patients whose best response is immune-related complete response (ir-CR) or immune-related partial response (ir-PR) as determined by irRECIST criteria.
3. Progression-free survival (PFS) is defined as the duration of time from start of treatment to time of progression or death, whichever occurs first. PFS rate at 6 months is the percentage of patients without disease progression at these time-point.
4. Overall survival (OS) is defined as the duration of time from start of treatment to death. OS rate at 6 months is the percentage of alive patients at these time-point
5. The duration of overall response is measured from the time measurement criteria are met for CR or PR (whichever is first recorded) until the first date that recurrent or progressive disease is objectively documented (taking as reference for progressive disease the smallest measurements recorded since the treatment started).

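### Section 5.4.2 takes a patient with unresolved axitinib toxicity off the study, while 5.9 and Table 6 footnote 6 allow the other drug and continued scans; no passage says which governs, so endpoint data could be lost

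*Combined protocol and SAP*

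**What the plan says.** Four places in the protocol bear on the same patient.

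- **Section 5.4.2 (axitinib dose modification).** The rule covers toxicity that the clinician ties specifically to axitinib and not to avelumab. Dosing is interrupted; if the event has not fallen to grade 2 or lower after 3 weeks, "then the patient should be withdrawn from the study and observed until resolution of the toxicity".
- **Section 5.9 (treatment duration).** "If patients develop unacceptable toxicity attributed to one of the study treatments leading to discontinuation, they could continue receiving the other study treatment".
- **Section 6, Table 6, footnote 6.** "For patients who discontinue treatment due to reasons other than disease progression, tumor assessment will continue as per during the treatment schedule", that is, every 8 weeks within a 7-day window. The long-term follow-up column of Table 6 also marks radiology and survival status, and footnote 5 collects this follow-up every 6 months by record review or phone.
- **Appendix 1, Subjective Progression.** "Every effort should be made to document PD even after discontinuation of study treatment".

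On analysis, section 9.1 states "All efficacy analyses will be performed in all eligible patients enrolled" and defines PFS as the "duration of time from start of treatment to time of progression or death, whichever occurs first". Neither 9.1 nor 9.2 gives a censoring rule for PFS. Appendix 1 requires CR and PR to be confirmed by two measurements at least 4 weeks apart.

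**The concern.** The event that triggers 5.4.2 lies inside the situation described in 5.9 and in footnote 6: treatment stopped for toxicity attributed to one drug, without progression. Under 5.4.2 the patient leaves the study, and the only observation named runs until the toxicity resolves. Under 5.9 and footnote 6 the same patient may stay on avelumab and goes on being scanned. Two investigators, each following the protocol, could handle identical patients differently.

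The trial decides on few events: section 9.2 rejects the regimen at 3 or fewer responses of 29 and accepts it otherwise. One unconfirmed response that is never rescanned could change that decision. PFS, duration of response and OS could also end early in patients selected by toxicity, and such a loss may be informative.

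**Working it through.** **1. Do the passages conflict, or can other text settle them?**

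| Question for a patient with axitinib toxicity above grade 2 after 3 weeks | 5.4.2 | 5.9 | Table 6 footnote 6 |
|---|---|---|---|
| In the study? | Withdrawn | Implied yes, if avelumab continues | Implied yes |
| Avelumab possible? | Leaves no room for it | Permitted | Not addressed |
| Tumor assessment | Not mentioned; observation until toxicity resolves | Not addressed | Every 8 weeks |

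No passage ranks these rules. The protocol can distinguish the two steps: for grade 3 or 4 infusion reactions, Table 3 withdraws the patient from study drug treatment rather than from the study, and 5.4.3 speaks of discontinuing axitinib. The wording of 5.4.2 therefore cannot simply be assumed to mean stopping the drug.

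**2. How a response could be missed (illustrative timeline).** Scans fall at weeks 8, 16, 24 and so on. Suppose a first PR at week 8 and an axitinib toxicity starting at week 9. The 3-week limit is reached at week 9 + 3 = 12. The next scheduled scan is at week 16, after withdrawal. If scanning stops at withdrawal, the PR stays unconfirmed.

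**3. The plan's own figures.** Inputs from section 9.2: null rate 0.05, target 0.20, 10 patients in stage 1, stop at 0 responses, 29 in total, reject at 3 or fewer.

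- Early stop = (1 − p)^10
- Expected N = 10 + 19 × (1 − early stop)
- Acceptance = Σ over x = 1 to 10 of P[Bin(10, p) = x] × P[Bin(19, p) ≥ max(0, 4 − x)]

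| True rate | Early stop | Expected N | Acceptance |
|---|---|---|---|
| 0.05 | 0.599 | 17.6 | 0.047 |
| 0.20 | 0.107 | 27.0 | 0.801 |

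These match the stated 60%, 10.7%, 17.6 and 27.0, and meet the stated error limits of 0.05 and 0.20.

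**4. Scale of a possible effect.** The documents do not say how often the 5.4.2 trigger would occur, so k is an assumption. Let k of 29 patients lose the chance of a confirmed response, independently of whether they would respond, and count as non-responders, as 9.1 implies. The effective response rate is 0.20 × (1 − k/29).

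| k | Effective rate | Early stop | Acceptance at true 0.20 |
|---|---|---|---|
| 0 | 0.200 | 0.107 | 0.801 |
| 1 | 0.193 | 0.117 | 0.778 |
| 2 | 0.186 | 0.127 | 0.754 |
| 3 | 0.179 | 0.139 | 0.727 |

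Section 9.2 counts 29 evaluable patients and does not define evaluable. If these patients were instead dropped without replacement and the cut-off of 4 responses kept, acceptance would be 0.786, 0.769 and 0.750 for k = 1, 2 and 3.

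**The case against.** The best reply is that 5.4.2 is a dose-modification rule, loosely worded. It does not say that scans or survival follow-up stop; observing the toxicity until it resolves adds a safety duty without cancelling others. Footnotes 5 and 6 and Appendix 1 set out follow-up after treatment, and the passages could be read together. This stands in part: the end of follow-up is a literal reading of 5.4.2, not stated text. It does not remove the conflict, because the protocol never says that a patient withdrawn from the study stays under footnote 6, and the difference from 5.9 over the other drug remains even on the generous reading.

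The denominator objection stands: 9.1 already keeps every eligible enrolled patient, so the patient does not drop out of the response-rate analysis under that rule. A response confirmed before withdrawal also stands, and a confirming scan may be obtained before withdrawal takes effect.

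A reader might take an event rate from the renal cell combination study in section 1.4: 4 of 55 patients stopped axitinib for adverse events, and 10 of 55 stopped one or both drugs. Neither measures this trigger. The first counts any adverse-event stop of axitinib, not toxicity still above grade 2 after 3 weeks. The second includes avelumab stops, which cannot trigger 5.4.2. Neither supports a forecast of the number affected or of the chance of at least one.

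**Conclusion.** The contradiction holds and rests on the text alone. Its effect on the endpoints is possible, not established. A reader might infer that the response rate is biased downward, or that PFS, duration of response and OS are censored for toxicity. The documents do not support either as fact: they give no censoring rule, footnotes 5 and 6 provide for the data, and a loss occurs only if sites follow 5.4.2 literally.

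Under the assumption of 1 to 3 affected patients counted as non-responders, the probability of accepting a truly 20% active regimen would fall from 0.80 to between 0.78 and 0.73. This is an upper-end effect, since it assumes that every would-be responder among them is lost. The point is worth correcting because the decision turns on 3 versus 4 responses and the correction is cheap. This review takes no position on whether avelumab should continue after such an event.

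**What to change.** - In 5.4.2, separate stopping study drug from leaving the study. State that, absent withdrawal of consent, the patient continues 8-weekly tumor assessments until progression (footnote 6) and survival follow-up (Table 6), and stays in the efficacy analysis under 9.1.
- Reconcile 5.4.2 with 5.9 so that one passage decides whether the other study drug may continue. Which rule that should be is for the investigator and sponsor.

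The cost is a short amendment touching two sections, plus continued assessments in what should be a few patients. Those assessments are already scheduled, so no new procedure is added.
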